#### **5.4 Dose Modifications and Dosing Delays**

No dose reductions of DARZALEX FASPRO are recommended. Consider withholding DARZALEX FASPRO to allow recovery of blood cell counts in the event of myelosuppression.

Medication will be discontinued for life threatening hypersensitivity reactions.

#### **5.5 Study Product Accountability**

Records of study medication used, dosages administered, and intervals between visits and the completion of the study should be captured in the Drug Accountability Form. This information must be captured in the source document at each patient visit.

At the conclusion of the study, and, as appropriate during the course of the study, all unused drug will be properly destroyed and discarded.

#### **5.6 Assessing Participant Compliance with Study Product Administration**

Regular monitoring will take place to assess participant compliance with completion of the questionnaires. Research coordinators will review Redcap to ensure questionnaires are completed in a timely manner when these questionnaires are being completed electronically (during the home infusion phase of the study).

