**Description of Intervention:**

- 1) All participants included in the study will receive daratumumab subcutaneous injection therapy (fixed dose 1800mg). On study, participants will receive 2 cycles of daratumumab in the infusion center, followed by 4 cycles at home followed by 2 more cycles at the infusion center. At the beginning of each cycle, patient reported outcome surveys and quality of life surveys will be collected (EORTC-QLQ-30, CTSQ, COST, and OOCAT). During the infusion center phase, administration will be given by an infusion center nurse. During the home infusion phase of the study a home infusion nurse will administer darzalex-faspro. During home administration, specific details on barriers to maintaining adherence will be collected and described with descriptive analysis (i.e. issues with storage, delivery, disposal of medication).

**Study Duration:** 36 months

**Participant Participation Duration:** 10 months

**Estimated Time to Complete Enrollment:** 26 months

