### Visit 1-2 C1D1 C2D1

Physical Exam, ECOG assessment, AE assessment  
Labs: CBC, CMP, SPEP/IFE, Serum Immunoglobulins, Serum Free Light Chains, Surveys: CTSQ, EORTC QLQ-30, COST survey, OOCAT (To be performed 3-5 days after the visit)

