## 6.2 Treatment Period

## Initial Visit (Visit 1, Day 1)

- Verify inclusion/exclusion criteria.
- Document any changes in Medical History, Concomitant Medications
- Perform and record physical exam findings.
- Document ECOG performance status
- Collect labs: CBC, CMP, SPEP, sFLC, Serum Immunoglobulins
- Document Current Multiple Myeloma Disease Status
- Complete the following surveys electronically (Surveys will be completed 3-5 days after the treatment day):
  - Cancer Treatment Satisfaction Survey
  - EORTC QLQ-C30
  - COST Survey
  - OOCAT Survey
- Administer DARZALEX FASPRO in the infusion center. No observation period needed.

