# 7 Study Procedures and Evaluations

## 7.1 Study Procedures/Evaluations

- Medical History – Includes documentation of the patient's medical history at time of enrollment and any changes that occur during the duration of the study.
- Medication History – Includes documentation of the patient's medication list at time of enrollment and any changes that occur during the duration of the study. Includes both prescription and over the counter medications.
- The following Questionnaires will be administered either in person and completed on a tablet or remotely through a link that will be distributed via the participants email.
  - Cancer Treatment Satisfaction Survey
  - EORTC QLQ-C30
  - COST Survey
  - OOCAT Survey
- Semi Structures Qualitative Interview will be conducted. Interviews will be conducted by a member of the research team. All interviews will be recorded and transcribed.
- Barrier Assessment of home administration of anti-neoplastic therapy.
  - Delay in anti-neoplastic therapy, delivery of medication, nurse arrival
  - Any wasted drug
  - Issues with storage or disposal of medication

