### 11.2 Analysis Plans

For primary analysis, the SWT domain CTSQ scores after all cycles will be analyzed jointly in a linear mixed effects model with a random effect of patient and the fixed effect of the delivery mode (home vs. infusion center). Log or other transformation of CTSQ scores will be used, as appropriate, to satisfy the model assumptions. Possible time trends will be considered in the model and incorporated, if significant. The mean difference in CTSQ scores between home and infusion center will be computed with the corresponding 95% confidence interval and tested (null hypothesis of zero mean difference) using appropriate model-based contrast with alpha 0.05.

The same approach will be used for the secondary analysis of other CTSQ domains, EORTC QLQ-30, COST survey, and OOCAT survey scores.

The adherence at the home setting cycles will be analyzed in repeated measures logistic regression model with a random effect of patient and the fixed effect of the delivery mode (home vs. infusion center). The model will be used to compute the average rate of home setting adherence with the corresponding 95% confidence interval.

---

Secondary endpoints related to the barriers to home administration and exploratory endpoints related to the patient perceptions of home based anti-neoplastic therapy will be summarized using descriptive statistics.

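### Sections 5.6 and 7.1 leave room for survey mode and completion chasing to follow the home-versus-center contrast, although Section 6.2 sets one rule for all eight visits

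*Combined protocol and SAP*

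**What the plan says.** Four places in the protocol govern how the questionnaires are collected.

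- **Section 5.6** begins with a general statement: "Regular monitoring will take place to assess participant compliance with completion of the questionnaires". It then describes the coordinators' REDCap review for timeliness, which applies "when these questionnaires are being completed electronically (during the home infusion phase of the study").
- **Section 7.1** says the questionnaires are "administered either in person and completed on a tablet or remotely through a link that will be distributed via the participants email". Neither route is assigned to a phase.
- **Section 6.2** gives the same instruction at center Visits 1, 2, 7 and 8 and at home Visits 3 to 6: "Complete the following surveys electronically (Surveys will be completed 3-5 days after the treatment day"). The study schematic agrees on timing for every visit: "CTSQ, EORTC QLQ-30, COST survey, OOCAT (To be performed 3-5 days after the visit").
- **Study Summary, Description of Intervention** is looser: "At the beginning of each cycle, patient reported outcome surveys and quality of life surveys will be collected".

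Every patient follows one sequence: two center cycles, four home cycles, two center cycles. The primary analysis in Section 11.2 is a linear mixed model of the CTSQ SWT domain score with "a random effect of patient and the fixed effect of the delivery mode (home vs. infusion center"). Time trends may be added. The model has no term for survey mode or setting.

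**The concern.** The primary outcome is self-reported satisfaction, and the exposure is where the dose is given. Section 5.6 equates electronic completion with the home phase, which implies some other practice in the center phase. Section 7.1 supplies a candidate: a tablet handed over in person. A site that works from these two sections could collect center-phase answers in clinic and home-phase answers by emailed link, with the REDCap timeliness review applied only to the latter.

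Setting and completeness of the primary outcome would then change at the same cycles as the exposure. The design has no randomization and no variation in sequence between patients, so a systematic difference in how people answer in clinic and at home would be read as an effect of home delivery. The same exposure applies to the other CTSQ domains and to the QLQ-30, COST and OOCAT scores, which use the same model. It could not be repaired after the data are collected.

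**Working it through.** **1. The passages side by side**

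| Aspect | Section 6.2 and schematic | Section 5.6 | Section 7.1 | Summary |
|---|---|---|---|---|
| Mode | Electronic at all 8 visits (6.2) | Electronic tied to home phase | In-person tablet or emailed link, no phase given | Not stated |
| Timing | 3 to 5 days after dosing, all 8 visits | Not stated | Not stated | Start of each cycle, both phases |
| Completion check | Not stated | General monitoring for all; REDCap review tied to home phase | Not stated | Not stated |

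The conflict is in mode and in the REDCap review. No study visit is scheduled 3 to 5 days after a center dose, so the in-person option in 7.1 has no obvious occasion except Day 1 in clinic, which lies outside the window in 6.2. That last step is an inference; the protocol does not say it.

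**2. Why the model cannot separate the two**

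If mode follows phase, its indicator is 0,0,1,1,1,1,0,0 over cycles 1 to 8 in every patient, identical to the delivery-mode indicator. The two effects are fully collinear. A time trend does not help, because it does not break that identity.

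**3. The plan's own figure**

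Inputs from Section 11.4: n = 20, difference 5.9, between-patient SD 13.76, correlation 0.79, two-sided alpha 0.05.

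- SD of within-patient differences = 13.76 × √(2 × (1 − 0.79)) = 13.76 × √0.42 = 8.92, as stated.
- Noncentrality = 5.9 / (8.92/√20) = 5.9 / 1.99 = 2.96. With 19 df, the noncentral t gives power 80.1%, against the stated 80%. It reproduces.

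**4. Precision with four cycles per site**

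Under compound symmetry, the SD of the difference between two four-cycle means is 13.76 × √(2 × 0.21/4) = 13.76 × √0.105 = 4.46, and the SE is 4.46/√20 = 1.00.

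**5. False-positive rate when a survey-mode shift b is fully aligned with site and the true site effect is zero**

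The sizes of b are assumptions. The rejection probability is the noncentral t (19 df) with noncentrality b/SE, both tails counted.

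| Assumed b (points) | Share of 5.9 | Protocol SD 8.92 (SE 1.99) | 4 v 4 cycles (SE 1.00) |
|---|---|---|---|
| 0 | 0% | 5% | 5% |
| 1 | 17% | 7.6% | 15.9% |
| 2 | 34% | 15.9% | 47.8% |
| 3 | 51% | 29.8% | 81.4% |

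The direction of any shift is also unknown. If it worked against home delivery, a true 5.9-point effect would be observed as 4.9, 3.9 or 2.9 points. Power on the SD of 8.92 would fall from 80% to 64%, 46% or 28%.

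**The case against.** The strongest reply is that the operative text is the visit schedule, and it is uniform. Section 6.2 repeats one instruction at all eight visits, and the schematic repeats the window. A tablet survey is itself electronic, so 7.1 does not contradict 6.2 on that word, and 7.1 does not assign its two routes to phases. The opening sentence of 5.6 promises completion monitoring without limit to a phase. On this view the parenthesis in 5.6 is a stray remark, and the confound appears only if a site departs from its own schedule at four visits. The shift sizes are also assumed.

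Most of this stands. It limits the point to an inconsistency that permits a confound. It does not remove the inconsistency: the REDCap review, the only completion check described in any detail, is tied to the home phase, and an in-person route is expressly allowed.

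A reader might go further and infer two things that the documents do not support.

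- *That timing differs by phase.* No passage sets a different time for the center phase. The Summary's wording covers both phases, and 3 to 5 days into a four-week cycle can loosely be called its beginning.
- *That surveys are completed before dosing and so rate the previous cycle's site.* No passage puts a survey before the dose. Halving the contrast (3/4 − 1/4 = 0.5, so 5.9 becomes 2.95, with power about 80% on SD 4.46) needs all eight surveys to be pre-dose, which is a uniform pattern and not a phase difference. If only the center surveys moved to pre-dose, only cycle 7 would be misassigned: 0.75 × 5.9 = 4.4 points, with power about 99%.

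**Conclusion.** The point holds as an internal inconsistency with a possible bias attached. Section 5.6, together with the in-person option in 7.1, does not fit 6.2. If 5.6 and 7.1 are followed, mode and completion chasing track the exposure, and the model in 11.2 cannot tell them apart.

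The size is conditional. It assumes no true site effect, a shift that follows site completely, and the planning values in 11.4. The protocol's SD of 8.92 gives the lower set of false-positive rates (8%, 16%, 30% for 1, 2, 3 points). Four cycles per site under compound symmetry gives the higher set (16%, 48%, 81%), because the more precise contrast is more sensitive to a fixed bias. Neither set predicts what will happen, since the documents do not say how large a survey-mode effect might be, or that one exists. The sample size calculation is not affected. The change is worth making because it is cheap and the bias, if it arises, cannot be removed later.

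**What to change.** Bring the other sections into line with Section 6.2:

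- **Sections 5.6 and 7.1:** state that all surveys in all eight cycles are completed by the same emailed REDCap link, 3 to 5 days after the dose. Delete the in-person tablet option.
- **Section 5.6:** remove the parenthesis limiting electronic completion to the home phase, and apply the coordinators' REDCap timeliness review to all eight cycles.
- **Study Summary:** replace the start-of-cycle wording with the same window.
- **Data capture:** record completion mode and date for every survey, and flag those outside the window.

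The cost is protocol wording; REDCap and the emailed link are already part of the plan. The one practical downside is that center-phase surveys may need reminders, because they can no longer be handed over during the visit.

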#### **5.7 Concomitant Medications/Treatments**

##### **5.7.1 Pre-dose Medications for Prevention of Injection Reactions**

All participants will receive the following medications 1 to 3 hours prior to each study drug administration:

- An antipyretic: paracetamol (acetaminophen) 650-1000 mg IV or PO
- An antihistamine: diphenhydramine 25-50 mg IV or PO or equivalent. Avoid IV use of promethazine.
  - After Cycle 6, if a participant has not developed an infusion-related reaction and is intolerant to antihistamines, modifications are acceptable as per investigator discretion.
- Corticosteroids (Long-acting or intermediate-acting):
  - Monotherapy: Methylprednisolone 100 mg, or equivalent, administered intravenously. Following the second infusion, the dose of corticosteroid may be reduced (oral or intravenous methylprednisolone 60 mg or equivalent).
  - Combination therapy:
    - Administer 20 mg dexamethasone (or equivalent) prior to every daratumumab infusion. When dexamethasone is the background regimen specific corticosteroid, the dexamethasone treatment dose will instead serve as pre-medication on daratumumab infusion days.
    - Dexamethasone is given orally or intravenously prior to the first daratumumab infusion and oral administration may be considered prior to subsequent infusions.
  - If the subject does not experience a major systemic administration-related reaction after the first 3 doses, consider discontinuing the administration of corticosteroids (excluding any background regimen-specific corticosteroid).
  - As per institutional guidelines, a leukotriene inhibitor (montelukast 10 mg PO or equivalent) is optional in Cycle 1 Day 1 and can be administered up to 24 hours before infusion as per investigator discretion.

If necessary, all PO pre-infusion medications may be administered out of the clinic on the day of the infusion, provided they are taken within 3 hours before administration. In the home setting, similarly, patients may take their premedication prior to the nurse arrival provided they are taken within 3 hours of Darzalex-Faspro administration.

#### 5.7.2 Post-dose Medication:

Administer post-infusion medication to reduce the risk of delayed infusion related reactions as follows:

- *Monotherapy studies:*
  - In an effort to prevent delayed infusion-related reactions, all participants will receive long- or intermediate-acting corticosteroid orally (20 mg methylprednisolone or equivalent in accordance with local standards) on the 2 days following all daratumumab infusions (beginning the day after the infusion).
  - In the absence of infusion related AEs after the first 3 infusions, post-infusion corticosteroids should be administered per investigator discretion.
- *Combination therapy:*

- Consider administering low-dose methylprednisolone ( $\leq 20$  mg) or equivalent, the day after the infusion. However, if a background regimen-specific corticosteroid (e.g. dexamethasone) is administered the day after the infusion, additional post-infusion steroids are not required, but may be considered by the investigator.
- **For all studies:**
  - For participants with a higher risk of respiratory complications (e.g. participants with mild asthma or participants with COPD who have an FEV1  $< 80\%$  at screening or developed FEV1  $< 80\%$  during the study without any medical history) the following post-infusion medication should be considered:
    - Antihistamine (diphenhydramine or equivalent)
    - Leukotriene inhibitor (montelukast or equivalent)
    - Short-acting  $\beta 2$  adrenergic receptor agonist such as salbutamol aerosol
    - Control medications for lung disease (e.g. inhaled corticosteroids  $\pm$  long-acting  $\beta 2$  adrenergic receptor agonists with asthma; long-acting bronchodilators such as tiotropium or salmeterol  $\pm$  inhaled corticosteroids for participants with COPD)
  - In addition, these at-risk participants may be hospitalized for monitoring for up to 2 nights after daratumumab administration. If participants are hospitalized, then an improvement in FEV1 should be performed and documented prior to discharge. If these participants are not hospitalized, then a follow-up telephone call should be made to monitor their condition within 48 hours after all infusions. If the participant has not experienced a significant medical event but is hospitalized overnight only for observation, then the hospitalization should not be reported as a serious adverse event. Investigators may prescribe bronchodilators, H1-antihistamines, and corticosteroids that are deemed necessary to provide adequate supportive care in the event a bronchospasm occurs after participants are released from the hospital/clinic. If an at-risk participant experiences no major infusion-related reactions, then these post-infusion medications may be waived after 4 doses at the investigator's discretion.
  - Any post-infusion medication will be administered after the infusion has completed.

### 5.7.3 Prophylaxis for Herpes Zoster

- Initiate antiviral prophylaxis to prevent herpes zoster reactivation within 1 week after starting DARZALEX FASPRO and continue for 3 months following the end of treatment

### 5.7.4 Prophylaxis and Management of Hepatitis B Reactivation

- Prophylaxis for Herpes Zoster Reactivation:
  - Prophylaxis for herpes zoster reactivation is recommended during the Treatment Phase, as per institutional guidelines. Initiate antiviral

prophylaxis to prevent herpes zoster reactivation within 1 week after starting study treatment and continue for 3 months following study treatment. Acceptable antiviral therapy includes acyclovir (eg 400 mg given orally 3 times a day, or 800 mg given orally 2 times a day or per institutional standards), famcyclovir (eg, 125 mg given orally, twice a day or per institutional standards), or valacyclovir (eg, 500 mg given orally, twice a day or per institutional standards), initiated within 1 week after the start of study drug.

- Management of Hepatitis B Virus Reactivation:
  - Primary antiviral prophylaxis is permitted as per local standard of care. Per protocol, HBV DNA testing by PCR is mandatory for participants at risk for HBV reactivation.
  - In patients who develop reactivation of HBV while on study treatment, suspend treatment with study treatment and any concomitant steroids, anti-neoplastic therapy, and institute appropriate treatment. Resumption of study treatment in patients whose HBV reactivation is adequately controlled should be discussed with physicians with expertise in managing HBV.

## 5.8 Dietary Restrictions

None

# 6 Study Schedule

## 6.1 Pretreatment Period/Screening

### Screening Visit (Day -30 to -1)

- Obtain and document consent from potential participant on study consent form.
- Review medical history to determine eligibility based on inclusion/exclusion criteria.
- Review medications history to determine eligibility based on inclusion/exclusion criteria.
- Perform medical examinations needed to determine eligibility.
- Document ECOG performance status
- Collect screening labs: CBC, CMP, SPEP, sFLC, Serum Immunoglobulins, Pregnancy Test (serum or urine) for women of child bearing potential
- Document Current Multiple Myeloma Disease Status
- Schedule study visits for individuals who are eligible and available for the duration of the study.

## 6.2 Treatment Period

## Initial Visit (Visit 1, Day 1)

- Verify inclusion/exclusion criteria.
- Document any changes in Medical History, Concomitant Medications
- Perform and record physical exam findings.
- Document ECOG performance status
- Collect labs: CBC, CMP, SPEP, sFLC, Serum Immunoglobulins
- Document Current Multiple Myeloma Disease Status
- Complete the following surveys electronically (Surveys will be completed 3-5 days after the treatment day):
  - Cancer Treatment Satisfaction Survey
  - EORTC QLQ-C30
  - COST Survey
  - OOCAT Survey
- Administer DARZALEX FASPRO in the infusion center. No observation period needed.

## Visit 2, Day 29 ± 3 days

- Record adverse events as reported by participant or observed by investigator.
- Document any changes in Medical History, Concomitant Medications
- Perform and record physical exam findings.
- Document ECOG performance status
- Collect labs: CBC, CMP, SPEP, sFLC, Serum Immunoglobulins
- Document Current Multiple Myeloma Disease Status
- Complete the following surveys electronically (Surveys will be completed 3-5 days after the treatment day):
  - Cancer Treatment Satisfaction Survey
  - EORTC QLQ-C30
  - COST Survey
  - OOCAT Survey
- Administer DARZALEX FASPRO in the infusion center. No observation period needed.

### Visit 3 Day 57 ± 3 days

- Record adverse events as reported by participant or observed by investigator (visit with provider may take place via telehealth).
- Document any changes in Medical History, Concomitant Medications
- Perform and record physical exam findings (may be limited if performed virtually) by APP or physician prior to home nursing visit.
- Document ECOG performance status
- Collect Cycle 3Day 1 labs: CBC, CMP, SPEP, sFLC, Serum Immunoglobulins, (Labs should be drawn 24-48 hours prior to injection date, can be collected in the patients home, local clinic, or at a local laboratory or at the main academic hospital)
- Document Current Multiple Myeloma Disease Status
- Complete the following surveys electronically (Surveys will be completed 3-5 days after the treatment day):
  - Cancer Treatment Satisfaction Survey
  - EORTC QLQ-C30
  - COST Survey
  - OOCAT Survey
- Barriers Assessment
  - Delay in anti-neoplastic therapy, delivery of medication, nurse arrival
  - Any wasted drug
  - Issues with storage or disposal of medication
  - Other issues that arise
- Patient to take Pre-meds prior to nurse arrival
- Administer DARZALEX FASPRO at home. No observation period needed.

